#### 9.6 Cohort Study Statistical considerations

#### 9.6.1 Sample size

The non-inferiority of birth in water compared to birth on land on rates of OASIS will be examined by parity. The Birthplace in England study found that overall 4.6% and 1.6% of nulliparous and parous women respectively, sustained OASIS. A sample size of 15,000 nulliparous and 15,000 parous 'low risk' women (7,500 each water and land) is required to obtain 90% power, and a 95% one-sided confidence interval around a treatment difference of zero. A non-inferiority margin of 1% or less,

Page **22** of **38** 

and 0.6% or less will be taken as clinically non-significant amongst nulliparous and parous 'low risk' women respectively. Since nulliparous women birthing in water are regarded as the least prevalent of the four groups, a data collection period providing data on 7,500 would ensure adequate numbers in the other three, more prevalent groups. These data will be combined to assess the effects averaged across both strata at an increased power, with a combined required sample size of 30,000 'low risk' women. We have assumed that 25% of the 6,600 waterbirths recorded in EuroKing® in 2015 were nulliparous women (1650/annum). Allowing for staggered site set-up, five years of combined retrospective and prospective data collection would be required (January 2015 – November 2020). The exact ratio of nulliparous and parous women who give birth in water will be determined once the retrospective data are examined, but with increasing numbers of waterbirths, with 18 of the 35 EuroKing® using sites, collectively undertaking 6,037 waterbirths in 2016, we are confident the study will have sufficient power to answer this important clinical question.

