#### 9.6.5 Primary analysis

The primary analyses are based on a non-inferiority test of birth in water versus on land, comparing 1) the proportion of mothers that have OASIS, and 2)the proportion of babies with a composite outcome of 'adverse neonatal outcome or treatment'.

To test the primary hypothesis of non-inferiority between birth in water and on land, the two outcomes will be evaluated for non-inferiority using logistic regression models, in the first instance with no adjustment for covariates. Adjusting for potential confounders may result in a more precise treatment effect estimate. The potential confounders of both primary outcomes (listed in table 1) will be considered and the impact on bias through conditional associations when conditioning on these covariates will be assessed using directed acyclic graphs (DAGs). The main logistic model will incorporate these selected covariates through regression adjustment. Results will be reported as an (unadjusted) odds ratio (birth in water compared to on land), and a two-sided 90% confidence interval (CI) for the (unadjusted and adjusted) odds ratio will be calculated. Non-inferiority will be concluded if the upper limit of the 90% CI for the difference in neonatal outcome between the groups is less than 1.0% (OR<1.21). Similarly, for the mother's outcome, non-inferiority will be concluded if the upper limit of the 90% CI for the difference in the proportion of OASIS between the groups is less than 1.0% (OR<1.23) in nulliparous 'low-risk' women and less than 0.6% (OR<1.38) in parous 'low-risk' women. The data will then be combined to assess the effects averaged across both strata.

If non-inferiority is shown, then a superiority analysis will be conducted as a secondary analysis of the primary outcomes using logistic regression and will be presented as an (unadjusted and adjusted) odds ratio of outcomes in the waterbirth group compared with the birth on land group. Parameter estimates will be provided alongside 95% CI and p-value. Secondary outcomes will have non-inferiority testing as detailed above.

	Maternal	Adverse neonatal
	outcome: OASIS	composite outcome
Maternal age (years)	√	$\checkmark$
Maternal BMI	✓	
Parity	√	
Duration of labour	✓	
Gestational age at delivery (weeks)	√	$\checkmark$
Child birth weight (g)	✓	$\checkmark$
Child head circumference (cms)	√	
Maternal thyroid disease (including hypothyroidism)		$\checkmark$
Pre-labour ruptured membranes		$\checkmark$

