#### 15.3 Sensitivity analysis

For both primary outcomes a number of sensitivity analyses will be performed to assess the robustness of the results to factors which may introduce bias.

Propensity score analysis: whether a woman who uses water immersion during labour remains in the pool for birth is likely to be influenced by their age, parity and other characteristics. This will result in imbalanced comparison groups. Incorporating propensity scores, i.e. the 'propensity' of a woman to choose a waterbirth, in the analysis is a way of controlling for this bias. It also allows a more detailed examination of the impact of imbalanced comparison groups on the results. Differences in baseline characteristics before and after propensity score matching will be examined and analyses re-run.

Instrumental variable analysis: Instrumental variables (IV) are factors associated with outcomes only via their association with exposure (in this case to birthing in water) and are independent of other factors associated with exposure. IVs can deal with the unobserved factors in selection bias and can add potential value to a study dealing with just observable factors. Such variables might include midwifery practice, or other factor that encapsulates unit culture. The capture of denominator data to provide information on the proportion of women using water for labour or birth at each unit, and the qualitative component of the study, will be utilised in this analysis.

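### Table 1 lists parity as a potential confounder for OASIS but not for the neonatal composite, so the main adjusted neonatal model omits a factor that the protocol expects to differ between the groups.

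*Protocol*

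**What the plan says.** Section 9.6.5 of the Protocol bases both primary analyses on logistic regression, first unadjusted and then adjusted. On the choice of covariates it says "The potential confounders of both primary outcomes (listed in table 1) will be considered", with directed acyclic graphs used to assess them, and then "The main logistic model will incorporate these selected covariates through regression adjustment". Table 1 is therefore the candidate list for the main adjusted model.

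In Table 1 the parity row has a tick under OASIS only. The neonatal column has nine ticks: maternal age, gestational age, birth weight, maternal thyroid disease, pre-labour ruptured membranes, intrapartum fever, fetal growth restriction, child gender and meconium-stained liquor.

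Two other sections bear on parity:

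- Section 15.3, introducing the propensity score analysis, says that whether a woman "remains in the pool for birth is likely to be influenced by their age, parity and other characteristics". It adds: "This will result in imbalanced comparison groups".
- Section 9.6.1 says "We have assumed that 25% of the 6,600 waterbirths recorded in EuroKing" in 2015 were to nulliparous women, and that "nulliparous women birthing in water are regarded as the least prevalent of the four groups".

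Parity enters the neonatal analysis in two other places: a planned subgroup (primary objective 2 in section 5.1, and section 9.6.6) and the propensity score sensitivity analysis (section 15.3).

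**The concern.** Section 15.3 names two characteristics likely to influence who stays in the pool: age and parity. Table 1 ticks age for both outcomes and parity for only one, and no reason is given for the difference. The protocol also treats parity as relevant to the neonatal outcome, since it plans to report that outcome by parity.

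If parity is related to the neonatal composite as well as to staying in the pool, leaving it out biases the pooled water-versus-land comparison. That comparison carries the decision that the upper 90% limit lies below 1.0% (OR<1.21). In a non-inferiority study of safety, a bias that is a sizeable fraction of the margin can change the conclusion. For OASIS the exposure is smaller: parity is a listed confounder there, and the margins are set separately by parity.

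**Working it through.** **1. The plan's own figure.** With a 5% rate in both groups, a 1.0-point margin, one-sided 5% and 90% power, the number per group is (1.645 + 1.282)² × 2 × 0.05 × 0.95 / 0.01² = 8,136. The protocol's 8,100 is reproduced, and power at 8,100 is 89.9%. The odds ratio for 6% against 5% is (0.06/0.94)/(0.05/0.95) = 1.213, which matches 1.21. None of these figures is in dispute.

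**2. Inputs for the size of the bias.**

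- Nulliparous share in water: 25% (section 9.6.1).
- Overall composite rate: 5%, with 8,100 babies per group (section 9.6.1).
- Nulliparous share on land, L: not given. Assumed 40%, 50% or 60%.
- Nulliparous-to-parous risk ratio for the composite, RR: not given. Assumed 1.25, 1.5 or 2.0.

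**3. Does section 9.6.1 imply a higher share on land?** With 8,100 in each group, nulliparous waterbirths number 0.25 × 8,100 = 2,025. If that is the smallest of the four parity-by-place cells, land must have more than 2,025 nulliparous women out of 8,100, so L exceeds 25%. This depends on roughly equal group sizes.

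**4. Spurious difference when waterbirth has no effect in either parity stratum.** Let m be the mean of the two nulliparous shares.

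- Risk in parous women: b = 0.05 / (1 + m(RR − 1))
- Land rate minus water rate: B = b × (RR − 1) × (L − 0.25)

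For L = 50% and RR = 1.5: m = 0.375, b = 0.05/1.1875 = 0.0421, and B = 0.0421 × 0.5 × 0.25 = 0.0053, or 0.53 points.

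| Land share | RR 1.25 | RR 1.5 | RR 2.0 |
|---|---|---|---|
| 40% | 0.17 | 0.32 | 0.57 |
| 50% | 0.29 | 0.53 | 0.91 |
| 60% | 0.40 | 0.72 | 1.23 |

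Entries are percentage points in favour of waterbirth, with no covariate adjustment. Fixing the land rate at 5%, instead of the overall rate, gives similar values: 0.50 in place of 0.53 for the central case, and 1.09 in place of 1.23 for the largest.

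**5. Direction.** B is zero if RR = 1 or if L = 25%. It reverses if RR is below 1. For example, RR = 0.8 with L = 50% gives b = 0.05/0.925 = 0.0541 and B = 0.0541 × (−0.2) × 0.25 = −0.27 points, which is against waterbirth.

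**6. Effect on the decision, unadjusted.** SE = √(2 × 0.05 × 0.95/8,100) = 0.342 points. If waterbirth is truly 1.0 point worse, the chance of declaring non-inferiority is Φ(B/SE − 1.645). That is 5% with no bias, about 46% at B = 0.53, and from 13% to 97% across the table.

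**The case against.** Four points can be made for the plan.

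- **Parity is handled elsewhere.** The sentence naming parity introduces a propensity score analysis planned for both primary outcomes to control this imbalance. Neonatal results by parity are also planned, and estimates within a stratum are not confounded by nulliparous versus parous status. This stands as mitigation, since a parity-driven result would probably be exposed. But the propensity analysis is a sensitivity analysis, and neither analysis puts parity into the pooled decision. The neonatal subgroup is also not described as powered, unlike the maternal one. With 2,025 nulliparous waterbirths against an assumed 4,050 on land and a 5% rate, power at the 1.0-point margin is about 52%.
- **Table 1 lists only potential confounders, subject to graph review.** The statistical analysis plan, not seen here, might add parity. That is possible, but section 9.6.5 describes selection from the listed covariates and no step for adding an unlisted one.
- **The imbalance is not established by cell counts alone.** With water at 1,650 nulliparous and 4,950 parous, and land at 2,000 and 8,000, nulliparous waterbirth is still the smallest cell, yet the land share is only 20%. This stands. Equal groups are a sample-size target, and section 7 limits the comparator to women who left the water for reasons other than clinical need.
- **The adjusted model is not the unadjusted one.** Maternal age, birth weight and other ticked covariates may carry part of the parity effect. This also stands.

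A reader might infer that the neonatal test is known to be biased towards waterbirth, with a false-pass rate near 46%. The documents do not support that. They do not link parity to the neonatal composite or give the land group's parity mix, and the 46% describes an unadjusted comparison under assumed values.

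**Conclusion.** The omission and its inconsistency with section 15.3 are in the text and do not depend on any assumption. As written, the main adjusted neonatal model leaves out a factor that the protocol itself expects to be imbalanced, and the other planned analyses do not correct the pooled estimate or its decision.

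The size and direction are conditional. If land has the higher nulliparous share and babies of nulliparous women are at higher risk, the bias favours waterbirth. Over the assumed ranges it is about 0.2 to 1.2 points against a 1.0-point margin. That range should be read as an approximate upper bound for the adjusted analysis.

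The case for listing parity holds whichever way the bias runs. It is a clear and easily made correction, not proof that the neonatal conclusion would be wrong.

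**What to change.** Tick parity in the neonatal column of Table 1 and include it in the main adjusted neonatal model. Keep the planned parity subgroup and propensity score analysis as supporting evidence. The unadjusted neonatal estimate will still carry any parity imbalance, so it should be read beside the adjusted one.

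The cost is one table entry and one model term. Parity is already needed for the OASIS model and for the subgroups, so no new data item is required and the 16,200 sample size stands.

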### **10** Qualitative Component

The qualitative component of the study will explore the influence of maternity unit culture on waterbirth and by placing the findings in the context of current NHS service provision will assist interpretation of the study's findings. Professional attitudes to waterbirth vary widely, with strong views held. It is therefore likely that aspects of unit culture may influence waterbirth rates. For example, differing professional perspectives may act as barriers or facilitators to birth in water, as may unit configuration and model of care (i.e. consultant-led or midwife-led), level of complexity of obstetric care provided, birth environment and facilities, staff training, local policies and procedures. There is currently no robust evidence describing these possible influencing factors.

The qualitative component will use a two-stage approach to identify and explore the influence of cultural factors, through collection and analysis of group and one-to-one interviews with a range of professional and lay stakeholders.

The key research questions are:

Page 26 of 38

- What factors influence birth pool use in units with high and low waterbirth rates?
- What factors influence giving birth in water in units with high and low waterbirth rates?

The term 'unit' refers to all births taking place within the NHS Trust or Health Board, whether within an institution or at home.

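### The confounder list behind both main models leaves out site and calendar period, although about 30 units are pooled and the protocol expects units to differ in waterbirth rates

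*Protocol*

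**What the plan says.** Protocol section 9.6.5 evaluates both primary outcomes with logistic regression, first unadjusted and then adjusted. The candidates for adjustment are those in Table 1, screened with directed acyclic graphs, after which "The main logistic model will incorporate these selected covariates through regression adjustment". For OASIS, Table 1 lists maternal age, BMI, parity, duration of labour, gestation, birth weight and head circumference. For the neonatal composite it lists maternal age, gestation, birth weight, thyroid disease, pre-labour ruptured membranes, intrapartum fever, growth restriction, sex and meconium. Every entry describes a woman or a baby.

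Section 7 pools around 30 NHS sites. The OASIS analysis uses births from January 2015 to November 2020; the neonatal primary outcome uses births from June 2018 to November 2020.

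Section 10 says: "It is therefore likely that aspects of unit culture may influence waterbirth rates". It names model of care, complexity of obstetric care, facilities, staff training and local policy as possible influences. Section 9.6.1 notes that waterbirth numbers are rising.

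Site appears in two other quantitative places. Section 9.6.6 will describe how the proportion using a pool at each site relates to adverse outcomes. The sensitivity analysis (numbered 15.3) considers instruments: "Such variables might include midwifery practice, or other factor that encapsulates unit culture". The propensity score in that section names age, parity and other characteristics.

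**The concern.** A factor confounds the comparison when it is related both to staying in the water for birth and to the recorded outcome. The protocol itself supplies the first half for unit. The second half is a reasonable inference. One component of the neonatal composite is antibiotic administration with or without proven infection, which is a treatment decision likely to depend on local policy. Detection of OASIS may depend on training and on how perineal examination is done. Either could also shift over calendar time.

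Screening with causal diagrams cannot repair this, because it selects from a list on which site and period do not appear. The other analyses do not repair it either: one is descriptive, one is an instrument still to be chosen, and the propensity score names no unit-level factor.

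The decision at stake is a safety conclusion on narrow margins: 1.0 point for OASIS in nulliparous women, 0.6 in parous women and 1.0 for the neonatal composite. If high-waterbirth units record fewer events, waterbirth looks safer than it is. If they record more, a true non-inferiority result may be missed.

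**Working it through.** **1. The plan's own figures.** Section 9.6.1 takes it that "overall 4.6% and 1.6% of nulliparous and parous women respectively, sustained OASIS", and assumes 5% for the neonatal composite. Power is 90% with a "95% one-sided confidence interval around a treatment difference of zero". With n per group = 2p(1−p)(1.645 + 1.282)²/margin²:

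| Outcome | p | Margin (points) | n per group, computed | Stated |
|---|---|---|---|---|
| OASIS, nulliparous | 4.6% | 1.0 | 7,517 | 7,500 |
| OASIS, parous | 1.6% | 0.6 | 7,491 | 7,500 |
| Neonatal composite | 5% | 1.0 | 8,136 | 8,100 |

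The odds-ratio margins also reproduce (1.23, 1.38, 1.21). So the sample sizes are sound on their own terms, and they contain no allowance for site. The neonatal standard error is √(2 × 0.05 × 0.95 / 8,100) = 0.342 points.

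**2. Bias if site is ignored (neonatal composite).** For sites of equal size with half of the births in water overall, the bias of the pooled difference is ρ × SD(waterbirth share) × SD(outcome rate) / (0.5 × 0.5), where ρ is the correlation between the two across sites. The protocol gives none of these three quantities; the values below are assumptions.

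| SD of share | SD of composite (points) | Bias at ρ = 0.3 | Bias at ρ = 0.5 |
|---|---|---|---|
| 0.10 | 1.0 | 0.12 | 0.20 |
| 0.15 | 1.5 | 0.27 | 0.45 |
| 0.20 | 2.0 | 0.48 | 0.80 |

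The sign of the bias is the sign of ρ, which is unknown.

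**3. Interval width with no systematic correlation.** With 30 sites the chance correlation has standard deviation 1/√29 = 0.186. This adds a random part of 0.186 × SD × SD / 0.25, and the one-sided error at the margin is Φ(−1.645 × 0.342 / total SE):

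- Low case: random part 0.074, total SE 0.35, error 5.4%.
- Mid case: random part 0.167, total SE 0.38, error 7.0%.
- High case: random part 0.297, total SE 0.45, error 10.7%.

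A second route uses the design effect 1 + (m−1) × ICC(outcome) × ICC(exposure). With 500 women per site in a parity stratum (540 babies for the neonatal outcome), assumed outcome ICCs of 0.001 to 0.01 and exposure ICCs of 0 to 0.10, the correct interval is 1.00 to 1.22 times the naive width (up to 1.24 neonatal). The error is 5.0% to 9.0% (9.2% neonatal). At 0.005 and 0.05 the width ratio in a parity stratum is 1.06 and the error 6.0%. If the waterbirth share is the same at every site, the naive interval is correct.

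**4. OASIS in nulliparous women, by simulation.** The settings were 30 sites of 500 women, assumed site-level SDs on the logit scale of 0.5 to 0.8 for waterbirth and 0.2 to 0.3 for OASIS, and 2,000 runs per setting.

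- Correlation −0.5, true difference 1.0 point: the crude difference is biased by about −0.20 to −0.45 points. Non-inferiority is wrongly concluded in roughly 15% to 37% of runs, against about 5% when stratified by site.
- Correlation +0.5, no true difference: power is roughly 49% to 74%, against 86% to 90% when stratified.

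**The case against.** The strongest reply is that clustering is routinely left to the statistical analysis plan, which is not at hand. For standard errors this stands: the protocol is silent on random effects and robust variance, and silence does not show that births will be treated as independent. It does not stand for confounders. Section 9.6.2 expressly defers missing data, whereas section 9.6.5 lists the confounders and says that selection is made from that list.

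A second reply is that nothing in the protocol shows outcome rates differing between units, and that the magnitudes rest on assumed between-site variation. Both are true. The figures show what could happen, not what will.

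A reader might also infer more than the text supports:

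- That unit culture drives waterbirth. Section 10 says only that an influence is likely.
- That both models span nearly six years. Only OASIS does; the neonatal model covers about two and a half years.
- That the case for calendar period is documented. Section 9.6.1 reports rising counts of waterbirths, which does not show that the share of low-risk pool users giving birth in water is changing.
- That unit is used only as an instrument. Section 9.6.6 also uses site, though descriptively.
- That the instrumental analysis must repeat the bias. Section 15.3 only suggests candidates. Midwifery practice could affect perineal trauma directly, which would break the protocol's own definition of an instrument, but this is a condition to be justified rather than a demonstrated failure.
- That birth setting should simply be added. If leaving the pool leads to transfer, setting at birth follows the exposure, and adjusting for it could introduce bias.

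**Conclusion.** The point holds as an omission from a stated list: Table 1 is too narrow for a comparison pooled over about 30 units that the protocol expects to differ in waterbirth rates. Its effect depends on units also differing in recorded outcomes, which is plausible but undocumented, and the direction cannot be determined.

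On the assumptions shown, the bias in the neonatal comparison is 0.12 to 0.80 points (mid case 0.27 to 0.45) against a margin of 1.0. This is the larger risk. Loss of interval coverage is secondary and more modest over most of the assumed range. It is tempting to read the plan as guaranteeing intervals that are too narrow, but that requires variation between sites in both exposure and outcome, and the analysis plan may handle it. The change should be made, because it protects a safety conclusion at almost no cost.

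**What to change.** - Add site and year of birth to Table 1 and to the adjustment set of both main models. Site can enter as fixed effects, or as a random intercept together with the site's mean exposure.
- State that the non-inferiority decision rests on intervals that allow for site.
- Add birth setting only as recorded at labour onset or pool entry, and only if that is available. The protocol does not show that it is.
- Use unit culture or midwifery practice as an instrument only with a written justification that it acts on outcome solely through waterbirth.

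Section 9.3 has data extracted site by site, so site and date of birth should already be in hand. The cost is a few more parameters, negligible against 16,200 babies and 30,000 women, and possibly a slightly wider interval.

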For the neonatal primary outcome, an estimate of 5% is used for the proportion of babies born to 'low risk' mothers experiencing 'adverse neonatal outcome or treatment'. A non-inferiority margin of 1.0% or less will be taken as clinically non-significant. A sample size of 16,200 babies (8,100 per group water / land) are required to have 90% power, and a 95% one sided confidence interval around a treatment difference of zero. The identification of women who leave and do not leave the pool prior to delivery of the placenta can only be captured by addition of new data items in the prospective cohort. As delivery of placenta in water, or postpartum haemorrhage of >1,000 ml following waterbirth are relatively uncommon events (17% and 1% respectively) the proposed sample size of 30,000 women who use a birth pool will be underpowered to detect a difference in these outcomes, but will be described.

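### The non-inferiority rule is worded on the risk difference, but the only interval promised is for the odds ratio, and the attached odds-ratio limits match the margins only at the planning rates

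*Protocol*

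**What the plan says.** **Sample size (Protocol 9.6.1).** All margins are absolute. For OASIS the planning rates are "overall 4.6% and 1.6% of nulliparous and parous women respectively, sustained OASIS". The margins are "A non-inferiority margin of 1% or less" for nulliparous women "and 0.6% or less will be taken as clinically non-significant amongst nulliparous and parous" women respectively. With 7,500 per group in each parity stratum, the size "is required to obtain 90% power, and a 95% one-sided confidence interval around a treatment difference of zero". For the neonatal composite, "an estimate of 5% is used for the proportion of babies born to" low-risk mothers with an adverse outcome, the margin is 1.0%, and "A sample size of 16,200 babies (8,100 per group water / land) are required to have 90% power". No odds ratio appears in this section.

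**Analysis (Protocol 9.6.5).** Both primary outcomes are tested by logistic regression, unadjusted first and then with selected covariates in the main model. The results are odds ratios with two-sided 90% CIs. The decision sentence then changes scale. For babies, non-inferiority follows if the "upper limit of the 90% CI for the difference in neonatal outcome between the groups is less than 1.0% (OR<1.21" in brackets. The OASIS criteria have the same form: a difference below 1.0% with OR<1.23 for nulliparous women, and below 0.6% with OR<1.38 for parous women.

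**The concern.** The rule names one scale, the model reports another, and each has its own threshold. The brackets present the two thresholds as interchangeable. They are not: a test on the log-odds scale has different power from a test on the difference at nominally the same margin, and the conversion holds at one comparator rate only.

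This is the decision rule for both primary safety outcomes. An analyst following 9.6.5 has an odds-ratio interval and an odds-ratio limit ready to use, and no stated interval for the quantity that the sentence names. The verdict could then depend on which reading is taken, possibly with the data already in view.

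**Working it through.** **Inputs** (Protocol 9.6.1 and 9.6.5). Order throughout: nulliparous OASIS / parous OASIS / neonatal.
- Planning rate p: 0.046 / 0.016 / 0.05
- Margin d: 0.010 / 0.006 / 0.010
- Size per group n: 7,500 / 7,500 / 8,100
- Odds-ratio limit: 1.23 / 1.38 / 1.21
- One-sided alpha 0.05 (z = 1.645), power 90% (z = 1.282), true difference zero

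**Step 1. Reproduce the stated sizes on the difference scale.**
n = 2p(1−p)(1.645 + 1.282)² / d² gives 7,517 / 7,491 / 8,136, against the stated 7,500 / 7,500 / 8,100. Power at the stated n is 89.9% / 90.0% / 89.9%. The 90% was therefore calculated for a test of the difference.

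**Step 2. Reproduce the bracketed odds ratios.**
OR = [(p+d)/(1−p−d)] / [p/(1−p)]
- 4.6% to 5.6%: 1.230
- 1.6% to 2.2%: 1.383
- 5% to 6%: 1.213

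The brackets are the absolute margins converted at the planning rates.

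**Step 3. Power if the odds-ratio limit decides.**
SE of the log odds ratio = √[2/(n p(1−p))]; power = Φ(ln(OR limit)/SE − 1.645).

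| | ln(limit) | SE | Power | Simulated | n per group for 90% |
|---|---|---|---|---|---|
| Nulliparous | 0.2070 | 0.0780 | 84.4% | 84% | about 9,110 |
| Parous | 0.3221 | 0.1301 | 79.7% | 80% | about 10,490 |
| Neonatal | 0.1906 | 0.0721 | 84.1% | 84% | about 9,920 |

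The simulation used 400,000 pairs of groups per outcome. Rounding of the limits explains little: with unrounded limits the powers are 84.5% / 80.2% / 84.9%. Taking the standard error at the margin instead of at the null gives 87% / 84% / 87%, still below 90%.

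**Step 4. Do the two rules agree on the same data?**
In the same simulations, at the planning rates with no true difference, 5.6% / 10.5% / 5.8% of studies passed the difference rule and failed the odds-ratio rule. The reverse was practically absent.

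**Step 5. Away from the planning rates.**
The documents give no other rates, so the range below is an assumption, for the neonatal outcome at 8,100 per group.

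| Assumed comparator rate | OR 1.21 as a difference | 1.0 point as an OR | Power, difference rule | Power, OR rule |
|---|---|---|---|---|
| 3% | 0.61 points | 1.35 | 98% | 66% |
| 4% | 0.80 points | 1.26 | 95% | 77% |
| 5% (planned) | 0.99 points | 1.21 | 90% | 84% |
| 8% | 1.52 points | 1.14 | 76% | 95% |

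Below the planned rate the odds-ratio limit is the stricter rule. Well above it, it is the looser one: at 8%, an upper limit of 1.5 points of excess harm would pass although the declared margin is 1.0.

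One further mismatch is not quantified here. The main model is covariate-adjusted, so its odds ratio is conditional, whereas the limits were converted from marginal rates.

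**The case against.** **The wording already names the difference.** In 9.6.5 the criterion is grammatically the CI for the difference, and 9.6.1 uses absolute margins only. Read so, the brackets are a translation and the 90% power stands. This carries weight. A reader might infer from Step 3 that the sample sizes are miscalculated, or that the study has 84% / 80% / 84% power as designed. The protocol does not support that: Step 1 reproduces the sizes, and the shortfall arises only if the odds-ratio limit is applied. The reading does not remove the defect, because 9.6.5 still promises no interval for the difference.

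**The group sizes are minima.** Section 9.6.1 sizes the study on its rarest cell, nulliparous waterbirths, and assumes 25% of waterbirths are to nulliparous women. If that split holds among low-risk women, 7,500 nulliparous imply 7,500 × 3 = 22,500 parous waterbirths. Against 7,500 parous land births, OR<1.38 then has 91.7% power by formula (90% simulated). Section 9.6.6 expects 15,000 pool births in the prospective period. If all are low-risk, against 8,100 land births, OR<1.21 has 91.4% by formula (91% simulated). This stands as a qualification for two of the three outcomes. The nulliparous cell is the one sized at its minimum.

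**Drift with the event rate is generic, and the planning rates may be apt.** A fixed 1.0-point margin also loosens in relative terms at low rates. A reader might infer that the planning rates come from an unselected population and must be wrong for this comparator. The protocol does not show that: it gives 5% as an estimate for babies of low-risk mothers, and the cited report cannot be checked here. Only the dependence on the rate is established.

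**How the interval is computed can sit in the SAP.** Agreed, and its absence from the protocol is not the point. The point is that the protocol fixes a rule on two scales that do not match.

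**Conclusion.** The point holds as an inconsistency in the decision rule, not as an error in any stated sample size. Section 9.6.5 decides on a difference, calculates an interval only for the odds ratio, and attaches odds-ratio limits as though they were equivalent.

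If the odds-ratio limits decide, power is about 84% / 80% / 84% rather than 90%, and the two rules give different verdicts in about 6% / 11% / 6% of studies with no true difference. These figures rest on the planning rates, the stated minimum equal groups, a Wald test and no covariate adjustment; power is higher if groups exceed the minimum. The neonatal range of 0.61 to 1.52 points rests on assumed comparator rates of 3% and 8%. If the difference decides, 90% power stands, and what remains is to state how its interval is obtained and to stop presenting the odds ratios as criteria.

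**What to change.** In section 9.6.5, state that the absolute risk difference is the sole decision scale, against 1.0 / 0.6 / 1.0 points. Obtain it with its 90% CI from the adjusted logistic model by marginal standardisation; the choice of interval method can go in the SAP. Remove the bracketed odds ratios as criteria: label them as conversions at 4.6%, 1.6% and 5%, and report odds ratios descriptively. This keeps the declared margins and the sample sizes in 9.6.1 as they are.

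If the odds-ratio limits are kept as the rule instead, restate power in 9.6.1 as about 84% / 80% / 84% at the stated sizes.

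The cost is a wording change and one standardisation step in the analysis, with no extra data.
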